12.2. Protection of volunteer's personal information

All documents and information related to this study, which will be provided by the investigator to the Sponsor, are strictly confidential. The investigator and other participants in the study will be obliged to use this information solely within the framework of this study to implement the Protocol.

The investigator must fill in and keep the Record of Enrolled/Screened/Randomized Volunteers, as well as other accounting records.

The investigator and the Sponsor should ensure protection of the personal data of the volunteers involved in the study. The required personal data of the study subjects (for example, social and demographic parameters) will be collected solely for the purpose of achievement of the study objectives and to a minimum extent.

No documentation identifying volunteers will be disclosed. Names of volunteers will not be disclosed to the third parties.

Before enrolment to the study, the volunteers will be introduced to the confidentiality provisions and use of their personal data, including the need for access by the monitor and other authorized persons (in cases of audits, inspections, etc.). These conditions will be reflected in the information for the volunteers.

12.3. Amendments to the Protocol

Any changes to the study plan should be agreed with the Sponsor, the State Expert Centre of the Ministry of Health of Ukraine and the Ethics Committee at the Healthcare Facility where the study will be conducted. Additions or amendments should be provided in writing, signed by all parties, dated and attached to the Protocol.

12.4. Agreement to the terms and conditions of the Protocol

The investigator conducting this study should not be entitled to deviate from the requirements of the Protocol and must confirm the agreement to work in accordance with this Protocol in writing. The contents of the Protocol cannot be disclosed to other individuals or entities without the written consent of the Sponsor.

12.5. Laws and regulations

The study will be conducted in compliance with the:

- 1) ICH Good Clinical Practice E6 (R2)
- 2) WMA Declaration of Helsinki – Ethical Principles for Medical Research Involving Human Subjects

13. DATA PROCESSING AND RECORD MAINTENANCE

13.1. Investigator File

The Sponsor of the study or its authorized representative is required to provide the Investigators with the documentation required for the clinical trial.

13.2. Data processing

The data that will be obtained by the investigator during the study will be recorded and kept in the CRF. After the verification procedures (monitoring and remote monitoring), the data will be processed for the statistical report.

13.3. Record maintenance and data protection

The investigator should ensure that the study documentation is retained until completion of the study. According to the contractual obligations, the investigator should keep the study documentation for at least 15 years.

Handling personal data of the volunteer and personal data of the investigator, which may be kept in the Sponsor's database, will be carried out in accordance with the Law of Ukraine On Personal Data Protection, as amended. When storing or processing personal data relating to the investigator and/or a volunteer, the Sponsor undertakes to take all necessary measures and precautions to ensure that the data is retained, and to prevent third parties from accessing them.

13.4. Amendments to the Protocol

The investigator should confirm his/her consent to work in accordance with the Protocol in writing. The investigator has no right to deviate from its requirements. During the study, corrections and additions that are considered as amendments can be made.

Amendments to the Protocol can be made after their approval by the local Ethics Committee at the SS. The history of all amendments to the Protocol should be kept on record.

14. FUNDING

Funding of activities related to the implementation of the provisions of this Protocol will be carried out by the Sponsor of the clinical trial on the basis of the concluded agreements between the Sponsor and the HCF, as well as between the Sponsor and the investigators.

15. PUBLICATION POLICY

The ownership of the data, outcomes, reports, findings, discoveries relating to this study belongs to the Sponsor. Therefore, the Sponsor has the right to use the data obtained during this study for any purpose, including filing for examination to the competent authorities in any other country.

The Sponsor's policy is aimed at promotion of presentation and/or publication of the findings of own studies using validated data, which will guarantee the reliability of the findings. The Sponsor approves the release of publications and may delay publication or communication for a limited period of time to protect the privacy or ownership of the information contained therein.

The ownership of the data, outcomes, reports, findings, discoveries relating to this study belongs to the Sponsor. Therefore, the Sponsor has the right to use the data obtained during this study for any purpose, including filing for examination to the competent authorities in any other country.

16. CONFIDENTIALITY OF INFORMATION

All materials, information (oral or written), and unpublished documents provided to the investigator (or any actions taken by the Company on its own behalf), in particular, this Protocol and the ICF, are the exclusive property of the Sponsor. The Investigator should treat all information provided to him/her or obtained during the investigation as confidential, and take all necessary measures to ensure that its confidentiality is preserved, except for the information to be disclosed in accordance with the legislation in force.

18. ATTACHMENTS

Attachment No. 1. Spielberger State-Trait Anxiety Inventory (STAI)

Attachment No. 2. Numeric character sets for mental calculation

Attachment No. 1. Spielberger State-Trait Anxiety Inventory (STAI)

Spielberger State-Trait Anxiety Inventory (STAI) Examination of the level of situational anxiety

Volunteer's ID: _____

Test time: _____:_____, _____/_____/_____
hours minutes day month year

Instructions: read each of the following sentences/statements carefully and cross out the number in the corresponding box on the right, depending on the way you feel at this time. Do not reflect on the questions for long, because there are no right or wrong answers.

No.	Statement	Never	Sometimes	Frequently	Almost always
1	Calm down	1	2	3	4
2	Safe	1	2	3	4
3	Tense	1	2	3	4
4	Annoyed	1	2	3	4
5	Comfortable	1	2	3	4
6	Upset	1	2	3	4
7	Concerned with future misfortunes	1	2	3	4
8	Relaxed	1	2	3	4
9	Anguished	1	2	3	4
10	At ease	1	2	3	4
11	Self-confidence	1	2	3	4
12	Nervous	1	2	3	4
13	Restless	1	2	3	4
14	Downhearted	1	2	3	4
15	Rested	1	2	3	4
16	Satisfied	1	2	3	4
17	Concerned	1	2	3	4
18	Stunned	1	2	3	4
19	Happy	1	2	3	4
20	I fell good	1	2	3	4

Volunteer's ID: _____

Processing of results

Calculate the total score based on answers given by volunteers.

While interpreting the results, use the following levels of anxiety:

- up to 30 points — low,
- 31 – 44 points — moderate;
- 45 and more — high.

Total score:_____

Key

Question No.	Answers			
	Never	Sometimes	Frequently	Almost always
1	4 points	1 point	3 points	2 points
2	4 points	1 point	3 points	2 points
3	1 points	4 points	2 points	3 points
4	1 point	4 points	2 points	3 points
5	4 points	1 point	3 points	2 points
6	1 point	4 points	2 points	3 points
7	1 point	4 points	2 points	3 points
8	4 points	1 point	3 points	2 points
9	1 point	4 points	2 points	3 points
10	4 points	1 point	3 points	2 points
11	4 points	1 point	3 points	2 points
12	1 point	4 points	2 points	3 points
13	1 point	4 points	2 points	3 points
14	1 point	4 points	2 points	3 points
15	4 points	1 point	3 points	2 points
16	4 points	1 point	3 points	2 points
17	1 point	4 points	2 points	3 points
18	1 point	4 points	2 points	3 points
19	4 points	1 point	3 points	2 points
20	4 points	1 point	3 points	2 points

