3. CLINICAL TRIAL OBJECTIVE

Primary objective: To assess the effect of the Pure Purr technology on the recovery of the autonomic nervous system in healthy volunteers affected by moderate stress.

Secondary objective: To assess the effect of 5-minute VR exposure on the situational anxiety parameters before and after moderate stress.

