5. INCLUSION AND EXCLUSION OF THE SUBJECTS

It is planned to enrol approximately 160 healthy volunteers to the study for further randomization of 100 volunteers.

For the purposes of randomization the volunteers should meet the inclusion criteria and have no non-inclusion criteria, be familiar with the terms of participation in the study, and sign the Informed Consent Form for participation in the study.

5.1. Inclusion criteria for the study subjects:

The study will enrol healthy volunteers meeting all the following inclusion criteria:

1. Females and males 20-60 years old;
2. Volunteers have no history of cardiovascular diseases;
3. Volunteers have no essential abnormalities of the ECG;
4. Normal or moderate level of situational anxiety based on the Spielberger State-Trait Anxiety Inventory (STAI);
5. Signed Informed Consent Form for participation in the study.

5.2. Non-inclusion criteria for the study subjects:

The study will not enrol volunteers meeting one or more non-inclusion criteria:

1. Intolerance to the VR technology;
2. HR above 110 bpm or below 50 bpm;
3. RR above 23 breaths per minute;
4. Abuse of alcohol, psychotropic substances and narcotic agents;
5. Smoking more than 100 cigarettes a week;
6. Administration of medicinal products for the treatment of cardiovascular and nervous system diseases 3 days prior to participation in the study;
7. Drinking tonics and energy drinks for at least 2 hours prior to participation in the study;
8. Severe or acute forms of respiratory, urogenital, gastrointestinal, haematological, metabolic, endocrine, or neurological diseases;
9. Mental disorders, which, in the opinion of the investigator, may distort the results of the study;
10. Participation in any clinical study over the last 3 months prior to enrolment to the study;
11. Parkinson's disease, Parkinson's symptoms, tremor, restless leg syndrome, and other motility disorders;
12. Pregnancy;
13. Any disease of the thyroid gland.

5.3. Exclusion criteria for the subjects:

The study will not enrol volunteers meeting one or more exclusion criteria:

1. Emergence of any medical condition, an adverse event or circumstances when, in the opinion of the investigator, it is not in the best interests of the volunteer to proceed with the participation;
2. Failure to comply with the requirements of the protocol;
3. Onset of one of the non-inclusion criteria.

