7. EFFICACY EVALUATION

7.1. Efficacy parameters

Principal and secondary parameters to be determined during the study:

Primary variable:

- Change in HF component after 5-minute exposure to the VR audio-visual sequence;

Secondary variables:

- Change in rMSSD after 5-minute exposure to the VR audio-visual sequence;
- Change in LF/HF ratio after 5-minute exposure to the VR audio-visual sequence;
- Change in SDNN after 5-minute exposure to the VR audio-visual sequence;
- Change in TP after 5-minute exposure to the VR audio-visual sequence;
- Change in HR after 5-minute exposure to the VR audio-visual sequence;
- Change in BP after 5-minute exposure to the VR audio-visual sequence;
- Change in Spielberger State-Trait Anxiety Inventory (STAI) score after 5-minute exposure to the VR audio-visual sequence.

The criterion for the prevailing efficiency for each variable is the presence of statistically significant differences between groups in favour of any of the groups with a directivity, which indicates the effectiveness of the technology. Procedures and methods required for efficacy evaluation are described in Section 4.13. The time and events schedule is shown in Section 4.12.

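### The STAI form asks about the present moment but offers frequency answers, so it is unclear whether the score reflects momentary or usual anxiety

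*Protocol*

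**What the plan says.** Protocol Section 3 gives the secondary objective: "To assess the effect of 5-minute VR exposure on the situational anxiety parameters before and after moderate stress". Section 7.1 serves it with one anxiety variable, "Change in Spielberger State-Trait Anxiety Inventory (STAI) score after 5-minute exposure to the VR audio-visual sequence". The synopsis and Section 4.1 likewise list no other anxiety measure. Inclusion criterion 4 in Section 5.1 uses the same inventory to admit only volunteers whose situational anxiety is normal or moderate. Sections 4.13 and 6.1 place the form at the eligibility check and after the VR session, following Stage 4.

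The form itself is Attachment No. 1. Its heading is "Examination of the level of situational anxiety". Its instruction asks for an answer "depending on the way you feel at this time". The 20 items are bare states such as Tense, Relaxed and Nervous. The answer columns read "Never Sometimes Frequently Almost always", and the scoring key on the next page carries the same four headings.

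**The concern.** The instruction and the answer scale ask different questions. The instruction asks about now; the columns ask how often. A volunteer who is slightly tense at that moment has no column that says so. One volunteer may treat the columns as a rough scale of strength, another may answer for how often he or she tends to be tense, and the form does not show which was done.

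The trial needs a score that can move within minutes and differ between two visits by the same person. If part of the score describes the person's usual state, that part is not expected to move. A finding of no difference between headsets on the STAI would then be hard to interpret, and the secondary objective has no other variable to fall back on. Screening under inclusion criterion 4 could also rest partly on usual anxiety.

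**Working it through.** The protocol gives no figure for this point, so the check is mainly one of text.

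1. **Time frame asked for.** The heading says situational anxiety, the instruction refers to the present, and the form records the test time in hours and minutes. All three point to the moment of completion.

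2. **Scale offered.** All four columns are frequencies, up to "Almost always". They appear on the form and again in the key, so this is not one stray label.

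3. **Any reconciliation elsewhere.** Sections 4.13, 4.14, 6.1, 7.1 and 9.2.3 say when the form is used or how quantitative variables are analysed. None offers answers graded by strength or explains how to give a frequency for a moment.

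4. **Direction of the effect.** Assume that a score S mixes momentary anxiety M and usual anxiety U, with an unknown share w between 0 and 1:

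   S = w·M + (1 − w)·U

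   If U is the same before and after the exposure and at both visits, it cancels from the differences:

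   - S(after) − S(before) = w·[M(after) − M(before)]
   - S(headset A) − S(headset B) = w·[M(headset A) − M(headset B)]

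   With w = 1 nothing is lost; with w = 0 no momentary signal remains. The same factor w stands in the numerator of the relative change defined in Section 9.2.3. The protocol gives no value for w, so only the direction, towards no difference, can be stated.

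5. **Whether the scoring key resolves it.** As printed, the key gives 4, 1, 3, 2 points across the columns for the 10 calm items and 1, 4, 2, 3 for the 10 anxious items. Never on all calm items with Almost always on all anxious items scores 10 × 4 + 10 × 3 = 70. Never on the calm items with only Sometimes on the anxious items scores 10 × 4 + 10 × 4 = 80. The key is therefore not ordered, which is a separate fault. Re-keying to 4, 3, 2, 1 and 1, 2, 3, 4 would repair the order, but the points would still be attached to how often. Correcting the key does not remove the mismatch.

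6. **Scope.** The sample size in Section 9.1 is calculated for HF only. With the table's rounded percentage points:

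   n = (1.96 + 1.64)² × 0.35² / [2 × (0.25 − 0.10)²] = 12.96 × 0.1225 / 0.045 = 35.3

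   Unrounded percentage points give 35.4. Either way n rounds up to the stated 36, and no STAI quantity enters. The primary endpoint comes from the ECG and is not affected.

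**The case against.** A reader might infer that the form measures habitual anxiety instead of momentary anxiety, that volunteers are forced to answer about themselves in general, and that a null STAI result would say nothing. The document does not support this. The form never asks about the usual or general state, and its heading, instruction and time field direct the volunteer to the present. Many volunteers may follow them and use the columns as a rough grading of strength. What remains is ambiguity, with attenuation possible but not shown.

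A reader might also turn the share w into a multiplier for the sample size. That would need an assumed w and an unchanged within-subject variance. The protocol gives neither. More stable answers could well lower that variance, and the random subject factor in Section 9.2.3 absorbs stable differences between people. The STAI also has no power target in Section 9.1. No such figure is offered here.

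The printed English may not be what volunteers see. Section 4.13 says that study information is given in Russian or Ukrainian, and the English form shows signs of translation, such as Calm down as the name of a feeling. The frequency headings could be a translation fault too. This stands as a reason to check the forms in use. It does not clear the current text, which is the only version in the protocol.

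Finally, each volunteer completes the same form with both headsets, so nothing suggests a bias in favour of either one, and the disordered key is the more clear-cut fault on these pages. Both remarks are fair. They limit the weight of the point but do not answer it.

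**Conclusion.** The point holds as a conflict between instruction and answer scale: the form does not settle whether a score reflects momentary or usual anxiety. To the extent that it reflects usual anxiety, the before/after and A-versus-B contrasts could be pulled towards no difference. The size is not derivable from the protocol.

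This rests on two assumptions: that the form in use carries the headings printed in English, and that at least some volunteers read them literally. The reach is the only measure of the secondary objective and one inclusion criterion. It is worth correcting before enrolment because, once forms are completed, no analysis can recover which time frame a volunteer had in mind.

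**What to change.** In Attachment No. 1, replace the four column headings, on the form and in the key, with ordered answers on how strongly the feeling is present now, so that they fit the existing instruction. Score them monotonically: rising with strength for the anxious items and falling for the calm items. The form's own instruction is sufficient ground for this; no outside version of the inventory is needed. Then confirm that every language version handed to volunteers carries the matching instruction and answers.

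The cost is one corrected attachment and a reprint before enrolment, with no added visit, procedure or volunteer. The key can be put in order in the same correction, but that alone is not enough.

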Testing the volunteers using the Spielberger STAI will be performed in the process of assessment of compliance with the inclusion/non-inclusion criteria, and upon completion of investigation of the virtual reality technology.

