4.14. Study data collection procedure

The study will be collected according to the following plan:

Visit 1.

The visit takes place at the SS and is considered to be Day 1 of the study.

Having received the informed consent for participation in the study, the investigator evaluates the compliance of the volunteer with the inclusion criteria and verifies that he/she has no non-inclusion criteria.

During the visit, the investigator:

- Obtains the Informed Consent Form from the volunteers;
- Checks the inclusion/non-inclusion criteria, evaluates the volunteers with the help the Spielberger STAI. In case a volunteer has all the inclusion criteria and no signs that meet the non-inclusion criteria, the investigator performs further data collection and randomization;
 - Anthropometric data (weight, height and body mass index);
 - Evaluates vital signs (BP, HR, RR, and body t°);
 - Physical examination;
 - Collects demographic data (date of birth, gender);
 - Collects clinical data on concomitant diseases, therapy and records them;
 - Investigates the technology of virtual reality (Stages 1, 2, 3, and 4);
 - Evaluates the volunteers' complaints in terms of the development of adverse events/adverse device effect (AE/ADE);
 - Evaluates tolerability;
 - The clinician records all indicators collected at Visit 1 and transfers them to the CRF.

Visit 2.

The visit takes place at the SS.

During the visit, the Investigator:

- Checks the inclusion criteria. In case a volunteer has no signs that meet the exclusion criteria, the Investigator performs further data collection;
 - Evaluates vital signs (BP, HR, RR, and body t°);
 - Evaluated physical signs;
 - Investigates the technology of virtual reality (Stages 1, 2, 3, and 4);
 - Evaluates volunteers based on the Spielberger State-Trait Anxiety Inventory (STAI);
 - The investigator records all indicators collected at Visit 2 and transfers them to the CRF;
 - Evaluates the volunteers' complaints in terms of the development of adverse events/adverse device effect (AE/ADE);
 - Evaluates tolerability;
 - Informs volunteers on study completion.

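### The STAI scoring key in Attachment No. 1 does not follow the order of its own answer headings, so totals scored from it as printed are usually wrong

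*Protocol*

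**What the plan says.** Attachment No. 1 contains the 20-item form, the anxiety bands and the scoring key. The form and the key carry the same answer headings in the same order, "Never Sometimes Frequently Almost always". Under these headings the key gives:

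- items 1, 2, 5, 8, 10, 11, 15, 16, 19 and 20 (calm wording, such as item 8, relaxed): "4 points 1 point 3 points 2 points"
- items 3, 4, 6, 7, 9, 12, 13, 14, 17 and 18 (tense wording, such as item 12, nervous): "1 point 4 points 2 points 3 points"

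The scoring instruction is "Calculate the total score based on answers given by volunteers". The total is then banded: up to 30 low, 31 to 44 moderate, 45 or more high.

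The total is used twice. Section 5.1, criterion 4 requires "Normal or moderate level of situational anxiety based on the Spielberger State-Trait Anxiety Inventory (STAI"). Section 7.1 lists as a secondary variable "Change in Spielberger State-Trait Anxiety Inventory (STAI) score after 5-minute exposure to the VR audio-visual sequence", which serves the secondary objective on situational anxiety in Section 3. No other part of the protocol restates or corrects the key.

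**The concern.** On an anxiety scale, points for a tense item should rise with frequency and points for a calm item should fall. The printed key does neither. Being tense sometimes earns 4 points, more than frequently (2) or almost always (3). Being calm sometimes earns 1 point, so it counts as less anxious than being calm frequently (3) or almost always (2). This can be seen from the item wording and the headings alone, without a manual for the instrument.

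If the key is applied as printed, two things go wrong. Volunteers can be placed on the wrong side of the cut-off at 45, so that some eligible people are turned away and some highly anxious ones admitted. And the STAI change can take the wrong sign, so that a fall in anxiety is reported as a rise. The endpoint can be rescored later from the marked answers. The enrolment decisions cannot be undone.

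**Working it through.** **Inputs** (all from Attachment No. 1), in heading order from 'Never' to 'Almost always':

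- Printed key: calm [4, 1, 3, 2], tense [1, 4, 2, 3]; 10 items of each type.
- Monotone key that keeps the printed points for 'Never': calm [4, 3, 2, 1], tense [1, 2, 3, 4].
- Bands: low up to 30, moderate 31–44, high 45 or more. A volunteer is taken as eligible at 44 or below, reading 'normal' in criterion 4 as the attachment's 'low'.

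**Where each column's points belong.** In both item types the points under 'Sometimes' belong to 'Almost always', those under 'Frequently' belong to 'Sometimes', and those under 'Almost always' belong to 'Frequently'. Three of four columns are displaced in all 20 rows. Of the 24 possible heading orders, only one (Never, then Almost always, then Sometimes, then Frequently) makes both rows monotone in the anxiety direction. One other order makes both monotone, but backwards. The correlation between [1, 2, 3, 4] and [1, 4, 2, 3] is 2.0/5 = 0.40.

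**Uniform patterns.** With one answer for all calm items and one for all tense items, total = 10 × calm points + 10 × tense points. The 16 patterns, as printed → monotone:

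| Calm \ Tense | Never | Sometimes | Frequently | Almost always |
|---|---|---|---|---|
| Never | 50 → 50 | 80 → 60 | 60 → 70 | 70 → 80 |
| Sometimes | 20 → 40 | 50 → 50 | **30 → 60** | **40 → 70** |
| Frequently | 40 → 30 | **70 → 40** | 50 → 50 | 60 → 60 |
| Almost always | 30 → 20 | **60 → 30** | 40 → 40 | 50 → 50 |

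- Total differs in 10 of 16.
- Level differs in 6: 20 → 40, 30 → 60, 40 → 70, 40 → 30, 70 → 40 and 60 → 30.
- Eligibility differs in 4 (bold). Wrongly excluded: 70 instead of 40, and 60 instead of 30. Wrongly admitted: 30 instead of 60, and 40 instead of 70. If only 'moderate' counted as eligible, 4 of 16 would also change.

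**Direction of change.** Moving a tense item from 'Frequently' to 'Sometimes' should change the score by 2 − 3 = −1; the printed key gives 4 − 2 = +2. Moving a calm item from 'Sometimes' to 'Frequently' should give 2 − 3 = −1; the printed key gives 3 − 1 = +2. Over all 20 items the true total falls from 60 to 40 (20 × −1 = −20), while the printed total rises from 30 to 70 (20 × +2 = +40). Of the 106 pairs of patterns with different monotone totals, the printed key reverses the order in 32 and ties 8.

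**Mixed answers, illustration only.** 100,000 simulated forms per scenario, with answers drawn independently. The percentages run from 'Never' to 'Almost always' and are assumptions, not protocol figures.

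| Assumed answers | Total differs | Correlation of totals | Eligibility differs |
|---|---|---|---|
| Calm items 5/15/35/45, tense 45/35/15/5 | 98.9% | 0.37 | 60.5% |
| All answers equally likely | 92.7% | 0.40 | 18.7% |
| Calm items 30/40/20/10, tense 10/20/40/30 | 97.5% | 0.28 | 13.6% |

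**The case against.** The strongest reply is that the protocol cannot show that anyone scored with this key. The text appears to be a translation: Section 4.13 offers volunteer information in Russian or Ukrainian, and a formula in Section 9.2.3 keeps Cyrillic subscripts. A single re-ordering of the headings puts every row right, which fits mislabelled columns in the English attachment as well as it fits a wrong scoring rule at the site. This stands. The misprint is certain; the harm is conditional.

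It is also true that the numbers 1 to 4 on the answer form are box labels, the same for calm and tense items, so a key that departs from them is not in itself a fault. The argument rests on the points not being monotone, and that is enough.

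The uniform patterns are extreme, 6 of the 16 totals are unchanged and eligibility is unchanged in 12. The share of real volunteers affected cannot be derived from the protocol.

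Finally, STAI is one of seven secondary variables, the primary HF variable is not scored with the key, and eligibility is settled before randomization. Misclassification therefore changes who is studied, not the within-subject headset comparison. This limits the reach of the error but does not make the key usable.

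A fault in reading the table from the PDF is unlikely, because the same permutation appears in all 20 rows and both item types. A look at the source page would settle it.

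**Conclusion.** The point holds: the key is wrong as written and must be corrected. Anyone who follows Attachment No. 1 as printed misplaces three of the four answer columns in every item and will usually get a wrong total, although some totals agree by cancellation. In the uniform patterns, 10 of 16 totals, 6 levels and 4 eligibility results change, and the sign of a change can reverse. These figures assume that the intended key is monotone from 'Never' to 'Almost always' with the printed points for 'Never' kept. The practical effect on this trial assumes that the printed key is the one used at the site.

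A separate and lesser matter is the timing of the inventory. Section 4.13 places it at the eligibility check and "upon completion of investigation of the virtual reality technology". The Visit 2 list in Section 4.14 has a single entry, "Evaluates volunteers based on the Spielberger State-Trait Anxiety Inventory (STAI"), after the test stages. Section 6.1 provides an assessment before and one after use of the headset. These passages need only be reconciled.

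**What to change.** 1. Confirm which headings and key the form used at the site carries, and check the source page of Attachment No. 1.
2. Correct the key so that, from 'Never' to 'Almost always', calm items score 4/3/2/1 and tense items 1/2/3/4.
3. If the misprinted key was applied to any form, rescore it from the raw answers and list every volunteer whose eligibility under criterion 4 changes.
4. Align the wording of Sections 4.13 and 4.14 with 6.1, so that each visit clearly has a before and an after STAI score.

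The cost is one corrected attachment page, a check of the site form and small wording changes. Rescoring is needed only if the misprinted key was used.
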